#### 1. PedEyeQ:

• The PedEyeQ is a patient-derived questionnaire designed to assess functional vision and eye-related quality of life. It consists of a child questionnaire for children ages 5 years and older, a proxy questionnaire completed by the parent regarding their child, and a parent questionnaire regarding the parent's own quality of life. The child questionnaire is administered by study personnel to children under the age of 8 years and is completed by the child for children 8 years of age or older (with the help of study personnel, if needed). Proxy and Parent questionnaires are completed by the parent. The questionnaires take about 10 minutes to complete.

# 2. Distance VA Testing (performed by a **masked** examiner prior to and at time of Primary Outcome):

 Monocular distance VA testing will be performed in the participant's current spectacle correction in each eye by a masked certified examiner using the electronic ATS-HOTV VA protocol for children <7 years and the E-ETDRS VA protocol for children ≥ 7 years on a study-certified acuity tester displaying single surrounded optotypes.

• The same VA protocol used at enrollment will be used throughout the study regardless of age at follow-up

- Repeat Distance VA Testing (performed by a masked examiner prior to and at time of Primary Outcome): Monocular distance VA testing will be performed in current refractive correction in each eye by a masked certified examiner (as above).
  - 4. Binocularity Testing (may be performed by an unmasked examiner)
    - Gross binocularity will be tested in current spectacle correction at near using the hand-held Worth 4-Shape test held at 40 cm.
    - Stereoacuity will be tested at near in current spectacle correction using both the Randot Butterfly and Randot Preschool stereoacuity tests.
  - 5. Ocular Alignment Testing (may be performed by an unmasked examiner)
    - Ocular alignment will be assessed in the current spectacle correction by the cover test, simultaneous prism and cover test (SPCT) (in cases of strabismus detected by cover test), and prism and alternate cover test (PACT) in primary gaze at distance (3 meters) and at near (1/3 meter).
  - 6. Contrast Sensitivity Testing (only at the time of the Primary Outcome visit; May be performed by an unmasked examiner)
    - Contrast sensitivity will be assessed in the current spectacle correction in each eye (right eye first then left eye) using the SpotChecks™ Contrast Sensitivity Test. Testing will be repeated in the left eye at the 8-week post-randomization visit, until there is sufficient sample size to perform test-retest reliability analysis.
  - 7. Adherence Monitoring: Adherence data from the ODM will be downloaded and compliance calendars will be reviewed.

The following additional testing is performed at the end of the visit when required as defined below in section 4.4.1.1.:

8. Cycloplegic Refraction (at the time of the Primary Outcome visit, if required by 4.4.1.1)

#### 4.4.1.1 Management of Refractive Error

- A cycloplegic refraction is mandated at the time of the primary outcome visit for participants if
- the previous amblyopic eye is still worse than the fellow eye (IOD > 0 and previously amblyopic
- eye worse based on average of test and re-test); or at the 56-week study visit if primary outcome
- has not been declared by the 48-week visit AND the previous amblyopic eye is still worse than
- the fellow eye (IOD > 0 and previously amblyopic eye worse based on average of test and re-
- 780 test).

751

752

753

754

755 756

757

758

759

760

761762

763

764

765

766 767

768

769 770

771

772 773

774

## 781 4.4.1.1.1 At Visits Prior to the 56-week Study Visit

- 782 If the new cycloplegic refraction compared to the old cycloplegic refraction differs by  $\geq 0.75$  D
- sphere or >0.75 D cylinder or >0.75 D in SE anisometropia or axis change of 6 degrees or more
- when cylinder is 1.00 D or more; then a change in spectacles is required. Whether to update the
- spectacles for smaller changes in refraction is at investigator discretion.
- When new spectacles are prescribed, the refractive correction prescribed must meet the
- requirements as described in section 2.3#4. The updated spectacles will be paid for by the study.
- All participants will continue study follow-up regardless of whether spectacles are changed or
- 789 not

# 4.4.1.1.2 At the 56-week Study Visit Since the 56-week study marks the end of the study, whether to update the spectacles is at

792 investigator discretion. Any change in spectacles will NOT be paid for by the study.

## **4.4.1.2. Masked Examiner**

The Masked Examiner must be certified to test visual acuity. Because the Masked Examiner must be masked to the participant's treatment group before primary outcome, he/she must be someone other than the managing investigator.

797 798

799

800

801

802

#### 4.4.2 Unscheduled Visits

Investigators may schedule additional visits at their own discretion. Participants will continue to follow the study-specified follow-up schedule regardless of any non-study visits. No data will be collected at non-study visits for the purpose of the study. Data from non-study visits will not be used to determine VA non-improvement ("stable/worsening") or whether the amblyopia is resolved or residual.

803 804

Investigators must not start any additional treatment (other than that outlined in *section 4.1 and 4.2*) prior to the 56-week outcome visit.

**CHAPTER 5.** Miscellaneous Considerations

808	
809	5.1 Contacts by the Jaeb Center for Health Research and Sites
810	The Jaeb Center serves as the PEDIG Coordinating Center. The Jaeb Center will be provided
811	with the parent's contact information. The Jaeb Center may contact the parents of the
812	participants. Permission for such contacts will be included in the Informed Consent Form. The
813	principal purpose of the contacts will be to develop and maintain rapport with the participant and
814	family and to help coordinate scheduling of the outcome examinations.
815	
816	5.2 Spectacles
817	Participants who have been screened and meet eligibility criteria while wearing trial frames with
818	the cycloplegic refraction at the screening exam will be provided spectacles paid for by the
819	study.
820	
821	Any change of spectacles will be paid for by the study.
822	
823	Contact lenses are not allowed during the study.
824	
825	5.3 Management of Strabismus
826	Strabismus surgery may be performed after the participant has been released to non-study
827	treatment. If surgery is performed, the date and type of surgery will be recorded in the comment
828	section of the Follow-up Examination Form. Note that participants should not be enrolled in the
829	study if strabismus surgery is planned or desired by families in the next 56 weeks (see exclusion
830	criteria section 2.4).
831	
832	5.4 Risks
833	
834	5.4.1 Risks of Examination Procedures
835	The procedures in this study are part of daily eye care practice in the United States and pose no
836	known risks. As part of a routine usual-care exam, the participant may receive
837	cycloplegic/dilating eye drops.
838	
839	5.4.2 Risks of Patching
840	If skin irritation occurs, the parent will be advised to put an emollient on the skin and discontinue
841	use of the patch for a day.
842	
843	Patching could potentially decrease the VA in the sound eye, although this is almost always
844	reversible and extremely unlikely when the sound eye has several hours without occlusion each
845	day. The diagnosis and management of reverse amblyopia is left to the Investigator's judgment.
846	
847	Patching could precipitate the development of an ocular deviation (strabismus), although this has
848	been found to be very rare in our previous studies and indistinguishable from the natural history
849	of amblyopia. If treatment precipitates the development of an ocular deviation (e.g., esotropia in
850	participants with hyperopia), the parent will be advised to have the child see the investigator as
851	soon as possible.
852	

853	5.5 Reporting of Adverse Events
854	No surgical procedures are part of the protocol. There are no expected long-term adverse events
855	associated with spectacles or patching. Investigators will abide by local IRB reporting
856	requirements.
057	•

857858

859

## 5.5.1 Risk Assessment

It is the investigators' opinion that the protocol's level of risk falls under DHHS 46.404 which is research not involving greater than minimal risk.

860 861 862

## **5.6 Participant Compensation**

Participant compensation will be specified in the informed consent form.

863 864 865

## 5.7 Participant Withdrawal

Participation in the study is voluntary, and a participant may withdraw at any time. For participants who withdraw, their data will be used up until the time of withdrawal.

867 868 869

866

## 5.8 Confidentiality

For security and confidentiality purposes, participants will be assigned an identifier that will be used instead of their name. Protected health information gathered for this study will be shared with the coordinating center, the Jaeb Center for Health Research in Tampa, FL. De-identified participant information may also be provided to research sites involved in the study.

ATS22ProtocolV7.0 (24Mar2023) ATS22ProtocolV7.0 (24Mar2023)PDF Page 47 of 66

## **CHAPTER 6.** Statistical Considerations

874 875 876

#### 6.1 **Statistical and Analytical Plans**

877

The approach to sample size and statistical analyses are summarized below.

878 879

## **6.2** Definition of Participant Cohorts

880 881 Two cohorts of participants with identical eligibility criteria, apart from age at time of randomization will be enrolled:

882 883

- Children aged 3 to <7 years at randomization referred to as the 'younger cohort'
- 884

• Children aged 7 to <13 years at randomization referred to as the 'older cohort'

885 886

887 888

889

890

891

892

Overall response to amblyopia treatment has been found to be somewhat reduced in children 7 years and older and it is likely that there are differences in adherence with spectacle correction and with prescribed patching between children <7 years and children 7 years and older; therefore, we believe that there could be a differential treatment effect between the two age cohorts. Recruitment potential is also expected to differ between the two age cohorts given the requirement for no prior treatment for amblyopia. Therefore, statistical considerations are different for the two age cohorts and all analyses described below will be conducted separately within each age cohort.

893 894

## **6.3** Primary Objective

895 896 897

898

899

The primary objective is to evaluate whether or not VA outcomes are equivalent after completion of up to 56 weeks of "sequential treatment" (spectacles first, with patching if needed for 2 hours per day/7 days per week) versus completion of up to 56 weeks of "simultaneous treatment" (spectacles together with patching 2 hours per day/7 days per week) in children newly diagnosed with amblyopia caused by anisometropia, strabismus, or both.

900 901

#### 6.4 Primary Efficacy Outcome – Distance Visual Acuity in Amblyopic Eye

902 903

904

The primary efficacy outcome will be mean change in amblyopic eye logMAR distance VA between randomization and completion of randomized treatment or at 56 weeks, whichever is earlier.

905 906 907

The outcome VA for each participant is defined as either of the following:

908 909 910

911

1. Amblyopic eye VA (calculated as mean of test and retest) at the last visit that was the basis for a "stable resolved" or "stable residual" determination (in the sequential group, stable residual amblyopia criteria can be reached only *after* patching has been instituted); or

912 913 914

915

2. 56-week visit amblyopic-eye VA (calculated as mean of test and retest) in those completing a 56-week visit without ever meeting criteria for "stable resolved" or "stable residual" amblyopia (if retest missing at 56 weeks, the single test value will be used).

The outcome VA for participants who never meet criteria for "stable resolved" or "stable residual" amblyopia and do not complete the 56-week visit, or receive non-randomized treatment for amblyopia prior to meeting criteria for "stable resolved" or "stable residual" amblyopia, will be imputed using multiple imputation based on amblyopic eye VA scores while on randomized treatment (using the mean of test and retest if done).

The primary analysis will follow the intent-to-treat (ITT) principle whereby all participants randomized will be included in the analysis according to the treatment group assigned at randomization. An analysis of covariance (ANCOVA) will be performed to compute the difference in mean change in amblyopic-eye distance VA (in logMAR lines) between the sequential and simultaneous treatment groups, adjusted for baseline amblyopic eye distance VA, and a 2-sided 95% confidence interval will be constructed on the treatment group difference. Equivalence of treatment groups will be declared if the upper and lower 95% CI limits are smaller (in absolute value) than the equivalence margin of 0.75 logMAR lines. Superiority of one treatment over the other will be declared if the upper and lower ends of the 95% CI exclude 0 difference.

 The ANCOVA model assumptions of normality and homoscedasticity (equal variance in treatment groups) will be checked, and if violated, an alternative method of analysis that is robust to the assumption(s) violated will be performed to check the sensitivity of the primary analysis model to the violation of assumptions. The methods to be considered include, but are not limited to, outcome VA transformation and the non-parametric randomization-based method of Koch et al. If results differ, the robust method will be used for trial conclusions and formulation of resulting recommendations.

Additional approaches to the primary analysis include the following:

• ITT with no imputation - Including only participants who meet the criteria for "stable resolved" or "stable residual" (only *after* patching has been instituted in the sequential group) or complete the 56-week visit (not including those for whom an outcome VA is imputed).

The multiple imputation ITT analysis is considered primary. If the ITT with no imputation and primary analyses give inconsistent results, exploratory analyses will be performed to evaluate possible factors contributing to the difference.

## **6.5** Secondary Efficacy Outcomes

All secondary outcomes involving amblyopic eye distance VA will use the ITT dataset with amblyopic eye distance VA imputed when missing. Secondary outcomes not involving amblyopic eye distance VA will use observed data, with no imputation for missing data.

For secondary outcome comparisons that are based on a parametric statistical model, all model assumptions will be checked, and if violated, data transformation or a non-parametric alternative will be used instead.

	JAEB CENTER FOR HEALTH RESEARCH
964	The distribution of all secondary outcomes will be tabulated at randomization and the outcome
965	visit for each randomized treatment group and described using descriptive statistics.
966	
967	Treatment group comparisons on secondary clinical outcomes will be controlled using the false
968	discovery rate (FDR) method at 5% and to adjust p-values and confidence intervals for
969	multiplicity.
970	
971	6.5.1 Pediatric Eye Questionnaire (PedEyeQ)
972	Rasch scores for each questionnaire item will be obtained from published look-up tables
973	available at www.pedig.net, and used to calculate a score for each participant and a separate
974	treatment group mean for each of the PedEyeQ domains of the Child, Proxy, and Parent
975	PedEyeQ at randomization and at each visit. Scores will also be converted to a 0-100 scale to
976	aid in interpretation.

976 977

978

979

980 981

982

983 984

985

986

987

988

989 990

991

992

- Child PedEyeQ:
  - Functional Vision
    - o Bothered by Eyes and Vision
  - Social
  - o Frustration / Worry
- Proxy PedEyeQ:
  - Functional Vision
  - o Bothered by Eyes and Vision
  - o Social
  - o Frustration / Worry
  - o Eye care
- Parent PedEyeO:
  - o Impact on Parent and Family
  - Worry about Child's Eye Condition
  - Worry about Self-perception and Interactions
  - Worry about Functional Vision

993 994 995

996 997

998

999

1000 1001

1002

Comparisons of interest, following the hypotheses detailed in the Background section are as follows:

- Comparison of domain scores between treatment groups at 8 weeks (the first follow-up visit, before the sequential group has the opportunity to start patching and is still in spectacle correction).
- Comparison of domain scores between treatment groups at the primary outcome visit defined as in *section 6.4*.
- Comparison of domain scores between treatment groups at the conclusion of the study (56 weeks).

1003 1004 1005

1006

Mean Rasch scores for each domain will be compared between randomized treatment groups using linear models, adjusting for baseline domain score and other baseline factors known to be associated with health-related quality of life (HRQOL).

All analyses will test the null hypothesis of no difference between treatment groups. The false discovery rate (FDR) method will be used to control the FDR at 5% and to adjust p-values and confidence intervals for multiplicity.

## 6.5.2 Proportion Achieving Stable Resolved Outcome with Spectacles Alone

The proportion of participants in the Sequential Spectacles group who achieve "stable resolved" outcome status with spectacles alone will be calculated, along with a 95% confidence interval.

#### 6.5.3 Binary Outcomes – Distance Visual Acuity

The proportion of participants who achieve the following binary outcomes will be tabulated by treatment group to aid in the interpretation of the primary outcome:

- The proportion of participants with outcome amblyopic-eye distance VA improvement of ≥ 2 logMAR lines (≥ 10 letters if E-ETDRS) from baseline.
- The proportion of participants with stable resolved VA (as defined in section 4.3.5).

Poisson regression with the log link will be used to estimate the relative risk of each outcome for the sequential versus simultaneous and an FDR-adjusted confidence interval. The Poisson models will include an adjustment for baseline amblyopic eye VA.

In the event the number of outcomes is too small for reliable estimation with Poisson regression,  a treatment group difference and 95% confidence interval will be estimated using the Farrington-Manning Score test or other exact method with no adjustment for baseline VA.

## 6.5.4 Time to Stable Resolved Amblyopia

For those participants who are classified as "stable resolved," the time from baseline to the time meeting that classification will be compared between treatment groups, using a Kaplan-Meier analysis with the logrank test.

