Primary Endpoint	
 
The primary efficacy endpoint will be mean change in amblyopic eye logMAR distance VA between randomization and VA at completion of randomized treatment or at 56 weeks, whichever is earlier.
 
The primary endpoint for each participant is defined as:
 
1. Amblyopic eye VA (calculated as mean of test and retest) at the last visit that was the basis for a "stable resolved" or "stable residual" determination (in the sequential group, stable residual amblyopia criteria can be reached only after patching has been instituted); or
 
2. Amblyopic-eye VA at 56 weeks (calculated as mean of test and retest) in those completing a 56 week visit without ever meeting criteria for "stable resolved" or "stable residual" amblyopia (if retest missing at 56 weeks, the single test value will be used).
 
To determine if the following endpoints differ between simultaneous treatment and sequential
 

Secondary Objectives/Endpoints	treatment groups.  Efficacy:  Child and parental health-related quality of life (HRQOL) domain scores as measured by PedEyeQ.  Proportion of participants with improvement of amblyopic eye distance VA of 2 or more logMAR lines (>=10 letters if E-ETDRS), using the primary endpoint as defined above.  Time to stable resolved amblyopia.  Amblyopic-eye distance VA (calculated as mean of test and retest) after 8 weeks.  Amblyopic-eye distance VA (calculated as mean of test and retest) at 56 weeks for all participants.  Binocularity by Randot Preschool Stereotest, Randot Butterfly Stereotest, and Worth 4 Shape Testing.  Monocular contrast sensitivity.  Safety:  Worsening of best-corrected fellow-eye distance VA of 0.2 logMAR lines or more at any time during the study from baseline (based on mean of test and retest, or initial test if retest not done).  Proportion of participants who develop a new strabismus.

	Proportion of participants who develop mild moderate and severe skin imitation from
	
 
Proportion of participants who develop mild, moderate, and severe skin irritation from patching.
 

	To evaluate the following endpoint within simultaneous treatment and sequential treatment groups:
	Recurrence of amblyopia in those who have resolved (defined as a 0.2 or more logMAR reduction and IOD of 0.2 logMAR or more from value at visit of resolution).

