## **6.12.4 Sample Size Estimation**

Based on previous data from ATS5 on sequential treatment (mean improvement of 3.7 logMAR lines) and data from Agervi et al (median improvement of 4 logMAR lines), we propose to design the present study to test whether the two treatments are equivalent, where equivalent is defined as a difference in mean improvement of less than 0.75 logMAR lines.

Assuming that the true difference in mean VA change between the two groups is 0 and assuming a pooled standard deviation of 1.7 logMAR lines, a total sample size of 272 participants (136 per group) has 90% power with a type I error rate of 2.5% to reject the null hypothesis of non-equivalence in favor of the alterative that simultaneous treatment is equivalent to sequential treatment (Table 3).

The percentage of participants lost to follow-up or withdrawn is expected to be small overall (10%) and equal between the two treatment groups. No adjustment to sample size has been made since outcome VA will be imputed for these participants (see *section 6.4*).

Table 3. Total Sample Size Estimates for a 2-Arm Study \*

SD of Change (LogMAR lines)	Treatment Group Difference in Mean VA Change from Baseline (logMAR lines) Equivalence Margin			
	<0.50	<0.75		
1.6	538	242		
1.7	606	272		
1.8	678	304		
1.9	756	338		

 \* The number of participants in cells represents the total number of participants required to reject a 2-sided null hypothesis that simultaneous treatment is not equivalent to sequential treatment by >=0.75 logMAR lines in favor of the alternative that simultaneous treatment is equivalent to sequential, with an equivalence margin of <0.75 logMAR lines; from 2 one sided T-tests with an alpha=0.025 and power 90% for a range of pooled SD of change in VA (logMAR lines).

A sample size of 272 participants for an equivalence study will have 90% power to reject a null hypothesis of no difference in favor of an alternative superiority hypothesis that there is a

- difference between groups, if the true difference between groups is as small as 0.67 logMAR lines of VA, with a type 1 error rate of 5%.
- 1334

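### Section 6.5.4 runs the time-to-stable-resolved log-rank test only on children who resolved, so it conditions on a post-randomization outcome and ignores how many children resolve

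*Protocol*

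**What the plan says.** The Protocol Summary lists "Time to stable resolved amblyopia" among the endpoints to be compared between the simultaneous and sequential groups, with no restriction on who is analysed.

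Section 6.5.4 defines the comparison: "For those participants who are classified as 'stable resolved,' the time from baseline to the time meeting that classification" is compared between groups "using a Kaplan-Meier analysis with the logrank test". It gives no censoring rule, and the set it defines contains nobody to censor.

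Two neighbouring provisions bear on this. Section 6.5 states: "All secondary outcomes involving amblyopic eye distance VA will use the ITT dataset". Stable resolved status is derived from amblyopic-eye and fellow-eye acuity (sections 4.3.2, 4.3.4 and 4.3.5), so it falls under that rule. Section 6.5.3 separately compares, across whole groups and by Poisson regression, the outcome it words as "The proportion of participants with stable resolved VA (as defined in section 4.3.5".

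**The concern.** Whether a child resolves is known only after randomization and may depend on the arm. Selecting on it breaks the randomized comparison. The denominator at each visit becomes the children who will eventually resolve, not the children who were randomized. An arm that adds late successes enlarges its own denominator at the early visits and so appears slower there, even when exactly as many of its children resolved early.

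The design makes late resolutions plausible in the sequential arm. Patching there starts only after acuity is stable with residual amblyopia on spectacles, so any child resolved by patching resolves later than one resolved by spectacles alone.

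Speed matters to the trial's rationale. Section 1.4 lists a possibly faster rate of improvement as an advantage of simultaneous treatment. If the primary result is equivalence, time to resolution could help a reader choose between the strategies. The false discovery rate adjustment in section 6.5 deals with multiplicity and does not correct selection.

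**Working it through.** **Arm size.** Section 6.5.4 gives no figure of its own, so the check uses the younger cohort's 136 per arm from section 6.12.4. That figure reproduces. With SD 1.7 lines, margin 0.75 lines, one-sided 2.5% tests, 90% power and true difference 0, n per arm = 2 × (1.7 × (1.960 + 1.645) / 0.75)² = 133.5, rounded up to 134 (268 in total). The noncentral-t calculation gives 90.4% power at 136 per arm.

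**Assumed resolution rates.** The documents give no visit-by-visit rates. The scenarios were set near the figures in section 1.2: at least 25-40% resolving with optical correction alone, and about 50% residual or recurrent after sequential treatment. Events occur at weeks 16, 24, 32, 40, 48 and 56. Week 8 is left out because a child starts with an interocular difference of at least 0.3 logMAR. To be non-improving (gain below 0.05) and within 0.1 at the first visit, the fellow eye would have to worsen by more than 0.15.

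Percentage first meeting stable resolved at each of the six visits:

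- Scenario 1: arm A 15, 10, 5, 3, 2, 0 (total 35); arm B 15, 10, 5, 8, 9, 8 (total 55).
- Scenario 2: arm A as in 1 (35); arm B 15, 10, 7, 6, 5, 2 (total 45).
- Scenario 3: arm A 20, 12, 7, 3, 2, 1 (total 45); arm B 20, 12, 9, 7, 7, 5 (total 60).

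Arm B's cumulative resolution is never below arm A's at any visit.

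**Mechanism by hand, scenario 1, week 16.** Each arm has 0.15 × 136 = 20.4 expected resolutions. Among all randomized, the hazard is 20.4/136 = 15% in both arms. Among resolvers only, the denominators are 0.35 × 136 = 47.6 and 0.55 × 136 = 74.8, so the hazards are 20.4/47.6 = 43% and 20.4/74.8 = 27%. The restricted test sees arm B lagging at a visit where the arms are identical. It also discards 272 − 122.4 = 149.6 children, or 55% of those randomized.

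**Mean time among resolvers, scenario 1.** Arm A: (16 × 0.15 + 24 × 0.10 + 32 × 0.05 + 40 × 0.03 + 48 × 0.02) / 0.35 = 8.56/0.35 = 24.5 weeks. Arm B: 18.40/0.55 = 33.5 weeks.

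**Simulation.** 3,000 trials per scenario, 136 per arm, two-sided 5%. The statistic is Z = (O − E)/√V, with E = Σ d·n₁/n and V = Σ d·(n₁/n)(1 − n₁/n)(n − d)/(n − 1) over event times. It was run once on resolvers only and once on all randomized children, with non-resolvers censored at 56 weeks. The Monte Carlo standard error near 57% is √(0.57 × 0.43/3000) = 0.9 percentage points.

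| Scenario | Mean weeks among resolvers, A vs B | Resolvers only: B called slower | All randomized: B called slower | All randomized: B called faster |
|---|---|---|---|---|
| 1: 35% vs 55% | 24.5 vs 33.5 | 99% | 0.0% | 80% |
| 2: 35% vs 45% | 24.5 vs 28.8 | 57% | 0.0% | 31% |
| 3: 45% vs 60% | 24.5 vs 29.9 | 77% | 0.0% | 52% |

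The resolvers-only test called arm B faster in 0% of trials in all three.

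In a further case both arms reach 30% by week 32 and one arm then adds 15% at weeks 40-56. The restricted test called the arm with more resolutions slower in 97% of trials, and the all-randomized test called it faster in 60%. Letting the other arm also resolve 5% late reduced the 97% to 75%.

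**Same timing, different proportions.** With 35% vs 55% resolving, the restricted test rejects in 5.1% of trials, which is chance, and the all-randomized test in 91%. With 40% vs 60% the figures are 4% and 91%.

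**Identical arms.** Both tests reject in about 5-6%.

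**Equal proportions, different timing.** Both arms reach 50%, with simultaneous earlier (2,000 trials, assumed timings). The restricted test calls sequential slower in 97% of trials, which is the right direction, and the all-randomized test in 10%. With a milder gap the figures are 31% and 4%. Another run with converging curves gave the all-randomized test 19% power.

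**The case against.** The strongest defence is that little depends on this test. It is one of many secondary endpoints. Section 6.5.3 already compares the proportion stable resolved across whole groups, so a difference in resolution would be seen. That stands and lowers the severity. It does not repair the log-rank p-value, which would still be reported as a comparison of speed.

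Naming Kaplan-Meier may suggest that censoring was intended. If so, the sentence misstates the intent and still needs correcting. This is more than detail left to a SAP: a SAP that follows the sentence repeats the flaw, and one that censors non-resolvers contradicts the protocol.

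A reader might infer that sequential treatment is expected to resolve more children, so that the test will reverse the answer. The documents do not support that. The simultaneous arm patches from randomization, section 1.4 raises possibly superior and faster outcomes for it, and section 6.12.1.2 expects equivalent acuity. Reversal needs one arm to resolve more children and to gain the extra ones late. The figures of 97% to 99% come from scenarios built to show this.

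The all-randomized test also has a real weakness. When final resolution is equal and the curves converge, its power for a pure speed difference is low. That does not make conditioning on resolution valid, but it is a reason to report the curves as well as the p-value.

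**Conclusion.** The concern holds as a should-fix on a secondary endpoint. As written, section 6.5.4 compares groups selected by their outcome, has no censoring, and conflicts with the ITT rule in section 6.5.

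The consequence depends on the pattern of resolution. With additional late resolutions in one arm, that arm was wrongly called slower in about 57% to 99% of simulated trials. With equal timing, the test rejected at chance level however different the proportions were. With equal proportions, it need not mislead. The percentages rest on assumed resolution rates and 136 per arm. The direction of the bias does not depend on the exact values.

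A reader might also infer that the trial's main conclusion is at risk. It is not: the primary equivalence analysis, its 0.75-line margin and N = 272 do not use this endpoint.

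**What to change.** Rewrite section 6.5.4, and carry the same text into the SAP, as follows:

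- All randomized participants in the cohort enter the Kaplan-Meier and log-rank analysis. The event is first meeting stable resolved. Those who never meet it are censored at their last study visit, which is 56 weeks for completers.
- State how the analysis handles children who first become stable residual on patching, and those who receive non-randomized treatment. Such children can remain in follow-up to 56 weeks, and release may come at different times in the two arms. One option is to keep them at risk to 56 weeks as never resolved on randomized treatment, with a sensitivity analysis that counts later resolutions.
- Report the cumulative proportion resolved at each 8-week visit by arm, so that an early speed difference stays visible if the curves converge.
- Keep times among resolvers as a descriptive summary without a test.

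The cost is a short paragraph and a decision on the handling of released children. No new data or visits are needed. The downside is the low power of the all-randomized log-rank for a pure timing difference when final resolution is equal.
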